Treating Where it Hurts: A randomized blinded clinical trial of local estrogen to the vulvar vestibule for dyspareunia in postmenopausal women

NCT03240081

13MAR2019

Principal Investigator: [name], MPH

eIRB #: 16770

1. Protocol Title

Treating Where it Hurts: A randomized blinded clinical trial of local estrogen to the vulvar vestibule for dyspareunia in postmenopausal women

2. Objectives

Purpose:

To perform a pilot study to evaluate the efficacy and safety of local estrogen therapy applied to the vulvar vestibule in a cohort of postmenopausal women with moderate or severe dyspareunia, and to examine the microscopic features of this condition before and after local estrogen therapy.

Primary goals:

- 1. To compare serum levels of β -estradiol before and during paired dosing of the hormone to the vulvar vestibule nightly.
- 2. To assess the comparative treatment efficacy of two strengths of β -estradiol dosed at an increased frequency to the vulvar vestibule.
- 3. To assess and characterize the microscopic features of tender vulvar vestibule tissues in postmenopausal women who have moderate to severe dyspareunia acquired since menopause.
- 4. To assess whether β-estradiol cream applied nightly for three months to the vulvar vestibule normalizes the microscopic profile of vestibule findings in parallel with correction of dyspareunia.

Hypotheses:

- 1. Topical estrogen to the vulvar vestibule is safe
 - a. β-estradiol serum levels associated with nightly estrogen applications to the vulvar vestibule will not be significantly different than levels published in studies of vaginal applications.
- 2. This condition is a form of vestibulodynia and will regress with topical estrogen therapy
 - a. For postmenopausal women with significant coital pain, vestibule biopsies will show neural hyperplasia and an infiltrate of lymphocytes, hallmarks of localized provoked vulvodynia, and doses of topical β -estradiol will be effective when applied to the zone of tenderness, the vestibule.
- 3. Nightly therapy to the vestibule will be more efficacious than published results of standard semiweekly vaginal therapy.
 - a. Nightly therapy will effect a correction of moderate/severe dyspareunia in greater than 62% of subjects, a published rate of correction using the standard treatment frequency to the vagina.

Primary endpoints:

- 1. Serum levels of β -estradiol before and during treatment with two strengths of cream applied locally to the vestibule.

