Whereas our prior RCT provided convincing data that the location of pain in postmenopausal dyspareunia is the vulvar vestibule, and that a non-hormonal therapy can be an effective palliative option, there is a major unmet need for data about corrective therapy. The only curative therapy for noxious postmenopausal vulvar symptoms is estrogen (Gass, 2013). Various female populations are in need of more complete information about risks and benefits of local estrogen therapy, as safety is a concern for both women who have no contraindication to estrogen and those who must balance risks of cancer recurrence. Herbenick documented that most young survivors of breast cancer wish for effective sexual enhancement products, demonstrating an unmet need in this population (Herbenick, 2008). That population presently numbers over 3 million women in the US (Natl Cancer Institute, 2013). A very recent ACOG Committee Opinion suggesting that vaginal estrogen therapy should be considered in survivors of estrogen-dependent breast cancer whose pain is refractory to non-hormonal remedies, because data does not show that use of local estrogen elevates rates of breast cancer recurrence (ACOG, 2016). This expert opinion, drawn from limited data on post-cancer vaginal estrogen, is an acknowledgement of the magnitude of the unmet need for effective therapy for dyspareunia in this breast cancer population. Our study will compare the serum levels achieved by vestibule dosing to serum levels from existing publications on the safety profile of estrogen products applied to the vagina.

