The study will include 50 subjects affected by dyspareunia and 5 reference cases (Total N=55). We estimate a need to screen 60 women in order to enroll 50 patients and we arrived at this estimate using the following considerations. We assume that all potential subjects who pass the phone screening and come for a screening examination having the complaint of postmenopausal dyspareunia will be found to have tenderness in the vulvar vestibule, as found in 100% of screened women in our previous study to locate the site of genital tenderness in a similar population (Goetsch, 2014). The prediction of how many women may be eliminated at screening comes from cautions regarding uterine issues. Although prior studies have indicated that use of local estrogen is without risk of stimulation to the uterus, we will be studying doses to an anatomic area with no prior data on absorption. We therefore feel it is important to screen candidates with a uterus to ensure that they enter the study with no evidence of thickening of the uterine lining, which can predispose to endometrial cancer. In women with a uterus, we will assess the width of endometrial stripes by transvaginal ultrasound. A 2011 British study of transvaginal endometrial screening found that 10-20% of asymptomatic women had a stripe width of 5 or more. (Jacobs, 2011) Those with a stripe ≥5mm will be excluded. The Oregon obesity prevalence is 29% (StateofObesity.org), defining a population at increased risk for endometrial thickening from adipose-related estrogen unopposed by any progestin. From a 2012 publication reporting the number of women in a Kaiser Permanente Northwest population who have had hysterectomies, we hypothesize that 26% of women screened will not have an intact uterus. (Lacie, 2012) Calculating the excess screens needed due to thickened endometrium in obese women and considering the proportion likely to have had hysterectomies, an estimated 60 women will be screened to enroll 50 subjects. All will be in the OHSU cohort.

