Subjects who do not speak English will not be enrolled.

9. Procedures Involved

This study includes up to 7 visits as outlined below:

Visit 1 (Screening Visit)

- Consent
- Review of inclusion/exclusion criteria
- Medical/surgical and medication history
- Pelvic examination to assess genital atrophy and vestibule tenderness

- Vestibule tenderness assessment will include the cotton-swab touch test (a test of mucosal sensitivity) and the lidocaine test (application of 4% aqueous lidocaine to tender mucosa for 3 minutes with reassessment of the cotton swab test to assess by what percentage the mucosal pain has been extinguished).
- The initial cotton swab used to map the tenderness in the vestibule and one from a vaginal side wall sample will be labeled, frozen and stored for later batched analysis of the microbiome composition.
- Transvaginal ultrasound to assess endometrial stripe thickness
 - Since subjects will have been selected because of having pain with vaginal penetration, it will be assumed that the vaginal probe used for the ultrasound examination will not be comfortable for the subject to insert without some preventative treatment. The study clinician will pre-treat the location of tenderness with 4% aqueous lidocaine for several minutes prior to insertion of the vaginal probe. This should prevent or minimize local pain from the vaginal probe.
- Blood sample collection for serum β-estradiol
- Completion of questionnaires
 - Demographics
 - Vulvar Pain Assessment Questionnaire (VPAQ), modified, #1
 - Lower Urinary Tract Symptoms (LUTS) questionnaire
- Randomization to study drug by Research Pharmacy, after all eligibility criteria confirmed by study staff
- Vulvar biopsy (for those subjects enrolling in the sub-study)
 - If participant agrees to biopsy, the baseline sample can be collected at either V1 or V2, dependent on subject preference
 - 4mm vestibule punch biopsy at the 4 or 8 o'clock site next to one of the Bartholin duct orifices after the zone has been pretreated with topical 5% lidocaine ointment for 10 minutes

Visit 2 (Enrollment/Randomization) - ***THIS VISIT MAY BE COMBINED WITH VISIT 1***

- Confirmation of inclusion/exclusion criteria
- Update to medical and medication history
- Dispensing of study drug with review of how to use/apply by study staff
- Dispensing of diary forms and review of instructions for documentation
- Dispensing of Tampons

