- The estrogen cream used in the study is similar to the FDA approved estradiol vaginal cream (ESTRACE). When estrogen cream is placed deep in the vagina in the same dose as the study cream, absorption is low and for most women blood levels remain the same as for those not using estrogen cream. If absorption takes place, side effects may include:
- Most Common:
 - Headache (13%)
- Less Common (1-10%):
 - Hot flushes
 - Breast tenderness
 - Vaginal infection (yeast infection, bacterial infection)

- Vaginal pain/discomfort
- Vaginal spotting
- Gastrointestinal complaints (abdominal pain, nausea, diarrhea)
- Urinary tract infection
- Hair loss
- Insomnia
- Anxiety
- Dizziness
- Changes in libido
- Back and joint pain
- Respiratory tract infection
- Discoloration of the skin
- Rare but Serious Side Effects (<1%)*
 - Endometrial cancer
 - Estrogen therapy may cause the lining of the uterus to grow and can increase the risk of uterine cancer. Because the amount of estrogen absorbed is low when using topical estrogen cream, the risk for uterine cancer is lower than when taking oral estrogen. You will have pelvic ultrasounds throughout the study to monitor the lining of the uterus.
 - Breast cancer
 - Estrogen therapy is associated with a small increased risk of breast cancer.
 - Cardiovascular disease
 - Estrogen therapy has been shown to increase the risk of heart disease including heart attack, stroke, and serious blood clots in some women.
 - Dementia
 - An increased risk of developing probable dementia in postmenopausal women 65 years of age or older has been reported in women receiving oral estrogen alone or estrogen combined with progestins.
 - As with any drug, allergic reactions may occur due to the study drug. These may range from mild to severe, can be life-threatening/fatal and include hives, difficulty breathing, and swelling of your face, lips, tongue, or throat. You should seek emergency medical treatment should you experience an allergic reaction.

b. Potential Benefits to Subjects

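### The only criterion for the serum safety hypothesis compares the cohort's absolute estradiol levels with published levels, which cannot show how many women absorb; each woman's change from her own pre-dose level is sampled but has no specified analysis

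*Combined protocol and SAP*

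**What the plan says.** - **Section 2, Hypotheses.** Hypothesis 1 is that vestibular estrogen is safe. Its single sub-item, 1a, is that serum levels on nightly treatment "will not be significantly different than levels published in studies of vaginal applications". No summary statistic, visit, published value or margin is given.
- **Section 3, Background.** The external comparison is repeated: "Our study will compare the serum levels achieved by vestibule dosing to serum levels from existing publications".
- **Section 2, Primary goals and Primary endpoints.** Goal 1 compares serum levels "before and during paired dosing of the hormone to the vulvar vestibule nightly". Primary endpoint 1 is serum levels "before and during treatment with two strengths of cream applied locally to the vestibule". Both name the pre-dose level.
- **Section 9, Procedures.** "Blood sample collection for serum β-estradiol" is listed at Visit 1 (before any dose), Visit 3 (12 hours after the first dose), Visit 4 (week 4) and Visit 6 (week 12).
- **Section 12, Data Analysis.** Pain score, biopsy, reference group and microbiome are covered. Serum estradiol is not.
- **Section 15a, Study Drug.** For cream placed deep in the vagina, "absorption is low and for most women blood levels remain the same as for those not using estrogen cream".
- **Section 5, Number of Subjects.** It states that uptake from this site has not been studied before. It also describes obese women as "defining a population at increased risk for endometrial thickening from adipose-related estrogen unopposed by any progestin".

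**The concern.** Whether vestibular dosing is safe in serum terms is a question about individuals: does any woman absorb, how many do, and by how much. Hypothesis 1a asks whether this cohort's levels resemble those of other women in other studies.

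That has two weaknesses. A cohort comparison can come out the same whether no woman absorbs or a minority absorbs substantially. And an absolute on-treatment level is the sum of absorbed drug, the woman's own estrogen and any calibration difference between the trial's laboratory and the published ones. A difference from published levels may therefore not be absorption, and the lack of one may not be lack of absorption.

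A woman's change from her own pre-dose sample avoids most of this. The trial collects the data for it, but ties no safety criterion and no analysis to it. Section 3 links the serum results to women who must weigh cancer recurrence, for whom individual exposure is what counts.

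**Working it through.** **The plan's own figures.** There is no estradiol sample size, power, margin or test to reproduce. The cohort was sized on pain: 25 per arm less 10% is 22.5 per arm, or 45 women. With SD 21.5 and a 20-point difference, an exact two-sided t-test at 0.05 has 85.4% power at 22 per arm and 87.0% at 23, which agrees with the stated figure of above 85%. It is used here only as the source of n = 45.

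**Assumed inputs (none are in the documents).** No-cream estradiol is log-normal, mean 5 and SD 3 pg/mL. Measurement noise has SD 1. The published group has 50 women. A share f of trial women rises by r pg/mL. Test: Welch, two-sided 0.05.

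**Step 1: size of the group shift.** For f = 10% and r = 20 the mean moves by f × r = 2 pg/mL.
- Variance in the trial group: 9 + 1 + 0.1 × 0.9 × 400 = 46.
- Published group without absorbers: 9 + 1 = 10. SE = √(46/45 + 10/50) = 1.11, so shift/SE = 1.81, below 1.96.
- Published group with 5% absorbers: the difference is 2 − 1 = 1 and the variance is 10 + 0.05 × 0.95 × 400 = 29. SE = √(46/45 + 29/50) = 1.27, so the ratio is 0.79.

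**Step 2: simulation (20,000 trials per row), share not significantly different from published.**

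| Trial women who absorb | Rise (pg/mL) | Published: none | Published: half as many | Published: equally many |
|---|---|---|---|---|
| 10% | 15 | 67% | 90% | 95% |
| 10% | 20 | 60% | 89% | 95% |
| 10% | 30 | 50% | 88% | 95% |
| 5% | 20 | 86% | 93% | 95% |

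The last column is the correct answer to 1a as worded, since the two groups really are alike. It is still silent on the number of absorbers.

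**Step 3: calibration.** With no absorption at all, a constant laboratory offset of 1 or 2 pg/mL makes the comparison significant in about 34% or 86% of trials (SE = √(10/45 + 10/50) = 0.65; ratios 1.54 and 3.08). A constant offset cancels from each woman's change.

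**Step 4: counting women.** The chance of enrolling at least one absorber among 45 is 1 − 0.9^45 = 99% at 10% and 1 − 0.95^45 = 90% at 5%. Counting women whose own rise exceeds 10 pg/mL finds at least one in 99% and 90% of simulated trials for rises of 15 to 30, and flags nobody when there is no absorption.

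**Step 5: form of the limit.** With no absorption, counting any on-treatment level above the 95th percentile of the trial's own Visit 1 levels flags about 3.9 of 45 women and almost never zero. A limit on level therefore picks up women with high natural estradiol. The limit has to be on the rise.

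**Step 6: precision.** For 0 of 45, the exact two-sided 95% upper limit is 1 − 0.025^(1/45) = 7.9%. For 0 of 22 in one arm it is 1 − 0.025^(1/22) = 15.4%.

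**The case against.** **The baseline is used.** A reader might infer that each woman's pre-dose level is discarded. The documents do not support that: goal 1 and primary endpoint 1 both call for levels before and during treatment. What stands is narrower. The safety hypothesis does not use the change, and section 12 says nothing on how it would be analysed.

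**The risk text is about another site.** A reader might take the section 15a sentence as an admission that some women absorb from the vestibule. It concerns deep vaginal placement and compares users with non-users. It supports variation between women by analogy only.

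**The 60% is not an error rate of 1a.** It requires a published group with no absorbers, whereas the section 15a sentence suggests that vaginal users may include some. This objection stands, and the figure is illustrative. But the more absorbers there are in the published group, the less the comparison reveals about this one.

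**No mean is specified.** Also true; that a group mean would be tested is an inference. A comparison described as not significantly different from published levels is nevertheless a cohort-level one, whatever the statistic.

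**Other safety data exist.** Endometrial thickness against baseline is primary endpoint 2, symptoms are reviewed at Visits 4 to 6, and a separate safety monitoring plan is cited but not available here. So the trial's whole safety assessment does not rest on 1a. The stated hypothesis of safety does.

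**Pairing is not a cure.** Correct: a paired test of mean change also dilutes a minority. With 10% absorbers rising by 2 to 5 between-woman SDs and 45 women, it is significant in only 19% to 52% of trials (within-woman correlation 0.5 to 0.8). The remedy therefore needs a count as well as a change.

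**Conclusion.** The point holds in this form: the sole criterion under hypothesis 1 cannot show how many women absorb and confounds drug with endogenous estrogen and calibration, while the within-woman data that could answer the question have no specified analysis.

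Under the stated assumptions, with 10% of women rising by 20 pg/mL, the criterion is met in about 60% to 95% of trials, depending on how many absorbers the published group contains. The direction follows from the design; the sizes rest on assumed levels, shares and rises. The documents do not show that any woman will absorb from the vestibule. They state that this is unknown, which is why the analysis should be able to detect it. For a pilot study this is a change that should be made, not a reason to doubt the design.

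**What to change.** In hypothesis 1a and section 12:

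1. Make the serum safety analysis each woman's rise from her own Visit 1 level at Visits 3, 4 and 6, with all her samples measured in the same assay run. Section 11 already plans batched analysis at one laboratory.
2. Report the median and maximum rise by strength.
3. Report the number of women whose own rise exceeds a limit fixed before results are seen, by strength and overall, with an exact 95% interval. State the limit as a within-woman rise, not as a percentile of Visit 1 levels. The 10 pg/mL used above is only illustrative; the investigators should set and justify the value.
4. Keep the comparison with published levels as descriptive context, and do not claim hypothesis 1 from it alone.

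The cost is wording, plus an instruction to the laboratory to keep each woman's samples together. No extra samples or visits are needed. The small downside is that a low count has a wide interval: even 0 of 45 leaves up to 7.9% of women possible.
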